## **13. Data handling and record keeping**

### **13.1 Data management**

Study data will be collected and managed using REDCap electronic data capture tools hosted at Queen Mary University of London. REDCap (Research Electronic Data Capture) is a secure, web-based application designed to support data capture for research studies, providing 1) an intuitive interface for validated data entry; 2) audit trails for tracking data manipulation and export procedures; 3) automated export procedures for seamless data downloads to common statistical packages; and 4) procedures for importing data from external sources.

Each major version of the CRF must be authorised by the Trial Steering Committee. Minor versions correcting typographical errors can be authorised by the Chief Investigator. All versions will be stored in the Trial Master File.

Each patient will be identified by a unique participant identification code. All person identifiable data will be logged on the Study Identification Log which will be part of the Investigator Site File, and used by the study team for participant contact. A study enrolment log will be maintained with pseudo-anonymised participant data.

Signed completed CRFs will be stored along with copies of source data (e.g. ambulance run sheet, medical records, clinical charts, drug charts) in the Investigator Site File which will be maintained in a secure location at St Bartholomew's Hospital. The CRF will be compliant with the CVCTU's Standard Operating Procedure for Trial Data Management. The Trial Master File (TMF) will be maintained by the CVCTU and kept in a secure, restricted access office within the William Harvey Research Institute.

### **13.2 Source data**

All versions of Consent Forms must be the authorised by the Sponsor and REC. All versions will be stored in the Trial Master File.

All original signed consent forms will be stored in the Investigator Site File. Copies will be scanned and inserted in the Cerner Millennium Electronic Health Record of Patients. The consenting procedure will follow the CVCTU's Standard Operating Procedure and the investigator taking consent will be trained in consent procedures and Good Clinical Practice (GCP).

If possible, source data will be collected directly into the REDCap. In the pre-hospital setting this will not be possible and data will be collected onto a paper CRF which will be transferred to the REDCap subsequently. A source data agreement will be written to specify where the source will be located. All source data will be kept securely in the participant study files within locked cabinets in restricted access rooms in St Bartholomew's Hospital.

All times will be recorded in Coordinated Universal time (UTC) to avoid confusion over transitions between British Summer Time and GMT. All times (e.g. medical devices, LAS dispatch desk, research clocks in study equipment, watches) will be assessed for accuracy against the time.is time server.

### **13.3 Confidentiality**

The investigators will preserve the confidentiality of participants taking part in the study in line with General Data Protection and Regulation and Data Protection Act (2018), NHS Caldicott principles, and UK Policy Framework for Health and Social Care. Data access will be granted to authorised representatives from the Sponsor, St Bartholomew's Hospital and any regulatory authority to permit monitoring, audits and inspections.

All paper files will be stored in locked cabinets in restricted access rooms.

Any electronic records of the data created during analysis of the study will not contain person identifiable data and will be stored on a network drive of Barts Health NHS Trust. Access to this area will be granted to the named study investigators.

The LAS provision of the Cardiac arrest database of matched controls (single data transfer) to the Chief Investigator after the end of the study recruitment will only include anonymised data, and data will be transferred between nhs.net emails to ensure data protection and confidentiality. Any missing data will be queried with the host establishment by the LAS team.

### **13.4 Record Retention and Archiving**

The Trial Master File will be stored securely for a minimum of 20 years after the study end (Section 7.9) and in accordance with the CVCTU's Standard Operating Procedure. The Chief Investigator will be responsible for the security of the data but may delegate this to any storage repository, approved by the JRMO.

All electronic copies of data will be deleted two years after publication of the study (Section 8.9).

The UK Policy Framework for Health and Social Care Research requires that research records are kept for 20 years after the project has completed. For studies sponsored by Barts Health NHS Trust the approved repository for long-term storage of local records is the Trust Corporate Records Centre. All research documentation must be archived in physical form – source data collected electronically will be printed and certified as authentic by the investigators. Electronic archiving is not accepted.

## **14. Laboratories**

### **14.1 Central and local laboratories**

The central laboratories for Barts Health NHS Trust will provide haematological, coagulation and biochemical assessments outlined in Table 2. The central and satellite Haematology, Blood Coagulation and Clinical Biochemistry laboratories have Certificates of Accreditation with Clinical Pathology Accreditation (UK) Ltd. The laboratories are also registered with UK National External Quality Assessment Services (UK NEQAS).

## 14.2 Sample collection, preparation and procedures

Blood samples will be taken as part of routine clinical practice. Therefore they will be requested, sampled, labelled and analysed according to the practices and policies at Barts Health NHS Trust for all clinical samples.

## 14.3 Sample storage and transfer

Excess serum and plasma are stored by the laboratories routinely for seven days to facilitate additional tests or confirmatory tests. These samples are stored at -20°C in the clinical laboratories. After the usual retention period for the clinical laboratories the excess serum and plasma will be transferred to the study team. Thereafter samples will be stored at -80°C. Samples will be labelled with the study ID and no patient identifiers. The chain of custody will be recorded in the Investigator Site File according to the study Standard Operating Procedures (Table 4). Subsequent analysis of these samples will require appropriate research approvals to be in place. All samples will be destroyed using standard laboratory procedures after 3 years.

# 15. Interventions and tools

## 15.1 Devices

The CARDIOHELP-i ECMO device (Maquet, Rastatt, Germany) is a CE marked device with an intended purpose which encompasses this investigation (see Table 6). Therefore, the Medicines and Healthcare products Regulatory Agency does not need to be notified about this study.

The CARDIOHELP-i device is classified in accordance with Council Directive 93/42/EEC concerning medical products, Appendix IX as a Class IIb device. It is defibrillator-protected Type CF in accordance with IEC 60601-1.

All devices will be submitted to Clinical/Medical Physics, Barts Health NHS Trust, for assessment according to the Trust policy on the management of medical equipment (CLI/POL/151/2014-001 or any superseding version).

The device will be used with an HLS Set Advanced 7.0 disposable. This is delivered sterile and pyrogen-free. It is stored in a cool, dark and dry place between 10-30 °C.

**Table 6** Intended purposes of the CARDIOHELP-i (Maquet)

Purpose	Description
Intended use	To drive, control, monitor and record an extracorporeal circulation For intra-hospital and inter-hospital patient transportation and for continuous operation
Intended user	Trained specialist medical staff
Intended patients	All patients independent of age, size and weight
Intended environments	Operating rooms, catheter laboratories, emergency departments and intensive care units In addition, the CARDIOHELP System can be used for intra-hospital and inter-hospital patient transportation in vehicles such as ambulances and aircraft as well as for emergency use outside a clinical environment

Taken from the Instructions for Use, Revision 1.5, Issued October 2014

## 15.2 Techniques and interventions

The suggested specific techniques for pre-hospital ECMO are outlined in the latest version of the Study Manual. This details:

- Team composition
- Daily checks and team preparedness
- Dispatch of the ECMO team
- Initial patient assessment
- Priming of the ECMO circuit
- Insertion of guidewires into the femoral vessels
- 20 minute time out procedure

- Cannulation of the femoral vessels and commencement of ECMO
- Post ECMO/ROSC care including transfer to the Heart Attack Centre
- Care at the Heart Attack Centre

### 15.3 Tools

#### 15.3.1 EQ-5D-5L

The EQ-5D-5L questionnaire will be used to assess quality of life in patients at 3 months [23]. This is a validated questionnaire and a license to deliver this questionnaire has been granted. Instructions for the use of this instrument are outlined in a trial Standard Operating Procedure (Table 4) to minimise inter-observer variations. We may administer the questionnaire using the usual ICU video-conference clinic, which has been established following the COVID-19 pandemic to reduce the need for vulnerable patients to travel to the hospital.

#### 15.3.2 Modified Rankin Scale of neurological assessment

The modified Rankin Scale will be used to assess neurological disability in patients at hospital discharge and 3 months [24]. Instructions for the use of this instrument are outlined in a trial Standard Operating Procedure (Table 4) to minimise inter-observer variations. We may administer the questionnaire using the usual ICU video-conference clinic, which has been established following the COVID-19 pandemic to reduce the need for vulnerable patients to travel to the hospital.

#### 15.3.3 Functional independence measure

The Functional Independence Measure is an internationally validate tool that will provide a detailed assessment of patients' functional status over the domains of self-care, sphincter control, transfers, locomotion, communication and social cognition [25]. Assessors will have undergone specific training in the use of the instrument and will follow the trial Standard Operating Procedure for its use (Table 4) to minimise inter-observer variations. We may administer the questionnaire using the usual ICU video-conference clinic, which has been established following the COVID-19 pandemic to reduce the need for vulnerable patients to travel to the hospital.

### 15.4 Non-investigational medicinal products (NIMPs)

The non-investigation medicinal products used in the study are outlined in Table 7. Many other drugs may be used in the care of the patient as dictated by the attending clinicians.

**Table 7** Non-investigational medicinal products

Medicinal product	Comments	Storage requirements
Oxygen/Medical air mixture	Sweep gas for ECMO circuit	Keep away from extremes of heat
Rocuronium bromide	As neuromuscular blockade	2-8°C
Teicoplanin	As antibiotic prophylaxis for surgical site infection	None
Heparin sodium	As an anticoagulant for ECMO	Below 25°C
Compound sodium lactate	For priming of the ECMO circuit	None

The pre-mixed oxygen/medical air mixture will be prepared as a special gas by the British Oxygen Company. It will be stored in accordance with the Health Technical Memorandum 02-01: Medical gas pipeline systems (Part B Operational management) produced by the Department of Health and outlined in the trial Standard Operating Procedure for the Management of medical gases. Specifically, a suitable storage area (BNB\_06\_071 in King George V Building, St Bartholomew's Hospital) has been approved by the trial pharmacist. A chain of custody will be maintained for all non-investigation medicinal products. A Summary of Product Characteristics (SPC) for each NIMP will be stored in the Trial Master File. The Undesired Effects outlined in these SPC will act as Reference Safety Information to enable attribution of causality and expectedness when classifying adverse events (Section 16.3).

## 16. Safety reporting

### 16.1 Adverse Events (AEs)

An AE is any untoward medical occurrence in a participant to whom an intervention has been administered, including occurrences which are not necessarily caused by or related to that intervention. An AE can therefore be any unfavourable or unintended sign (including an abnormal laboratory finding), symptom or disease temporally associated with study activities.

### 16.2 Adverse Reaction (ARs)

An AR is any untoward and unintended response in a participant to an intervention. All adverse events judged by either the reporting investigator or the sponsor as having a reasonable causal relationship to the intervention qualify as adverse reactions. The expression 'reasonable causal relationship' means in general that there is evidence or an argument to suggest a causal relationship.

### 16.3 Classification of Adverse Events and Reactions

A serious adverse event (SAE) is defined as an untoward occurrence that:

- Results in death,
- Is life-threatening,
- Requires hospitalisation or prolongation of existing hospitalisation,
- Results in persistent or significant disability or incapacity,
- Consists of a congenital anomaly or birth defect, or
- Is otherwise considered medically significant by the investigator.

All Serious Adverse Events will be assessed for causality and expectedness, using the definitions in Table 8 and Table 9. Reference Safety Information for this assessment is included in Table 9 and Summary of Product Characteristics for the NIMPS outlined in Table 7.

---

**Table 8** Definitions of relationship of an SAE to study intervention

Relationship	Definition
Unrelated	There is no evidence of any causal relationship
Related, Unlikely	There is little evidence to suggest there is a causal relationship (e.g. the event did not occur within a reasonable time after administration of the trial medication). There is another reasonable explanation for the event (e.g. the patient's clinical condition, other concomitant treatment).
Possibly	There is some evidence to suggest a causal relationship (e.g. because the event occurs within a reasonable time after administration of the trial medication). However, the influence of other factors may have contributed to the event (e.g. the patient's clinical condition, other concomitant treatments).
Probably	There is evidence to suggest a causal relationship and the influence of other factors is unlikely.
Definitely	There is clear evidence to suggest a causal relationship and other possible contributing factors can be ruled out.
Not assessable	There is insufficient or incomplete evidence to make a clinical judgement of the causal relationship.

---

**Table 9** Definitions of expectedness of an SAE for the study intervention

Expectedness	Definition
Unexpected	Unexpected events are those not anticipated but could relate to the study. Events that are of a more serious form that would be expected should also be considered as unexpected.

Expected	
Expected events are:
 
 
-Failure to cannulate a patient for ECMO
 
-Hypoxic brain injury
 
-Death due to myocardial failure
 
-Death due to hypoxic brain injury
 
-Vascular damage during cannulation in adverse environment
 
-Bleeding at site of cannulation
 
-Infection at site of cannulation
 
-Intracranial haemorrhage
 
-Gastrointestinal haemorrhage
 
-Events outlined in the Undesired Effects section of the SPC for each NIMP
 

----------	--

## 16.4 Notification and reporting of Adverse Events and Reactions

If the AE is not defined as serious (see Section 16.3), the AE will be recorded in the study documents, and the participant followed up by the research team. The AE will be documented in the participants' source documents, the electronic Case Report Form (CRF) in REDCap, and, where appropriate, medical records.

Medical judgement will be exercised in deciding whether an AE is serious in other situations. Important AEs that are not immediately life-threatening or do not result in death or hospitalisation but may jeopardise the subject or may require intervention to prevent one of the other outcomes listed in the definition above, should also be considered serious.

## 16.5 Notification and reporting of Serious Adverse Events

SAEs will be reported to the REC where in the opinion of the Chief Investigator the event was serious and:

- Related (it may have resulted from administration of any of the research interventions), and
- Unexpected (the type of event is not listed in Table 9).

All SAEs will be reported to the CVCTU within 24 hours of site notification via the REDCap SAE eCRF, and will be recorded in the study SAE log and will constitute part of the routine statutory safety reporting to the Research Ethics Committee (REC). Serious Adverse Events (SAEs) that are considered to be 'related' and 'unexpected' will be reported to the sponsor within 24 hours of learning of the event, and to the REC within 15 days in line with the required timeframe. Any additional relevant information must be reported within 8 days of sending the first report.

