Adverse climate Wind, cold, and rain may make the cannulation difficult.	2	3	6	Use of IPX4 standard equipment if possible to counter effects of rain. Covers utilised for other equipment. Weights for drapes to counter wind Suspension of service if conditions considered too adverse to safely deliver pre-hospital ECMO	2	2	4

Adverse publicity for Trust/Organisations involved An adverse outcome for the patient (severe neurological injury but survival; or death despite significant and prolonged intervention) may be perceived in retrospect as an inappropriate use of healthcare resource (e.g. ICU capacity, blood products).	2	3	6	Discussion with Communications team prior to the event – avoid all public comments until patient outcome known and consent of patient gained. Aim to undertake resuscitation out of public view	2	2	4
Reduced capacity to support other patients Any patient will take up ICU capacity in terms of bed spaces, staffing, and equipment. This may limit the ability to support the work of elective cardiac surgery or emergency respiratory ECMO.	2	3	6	Pre-hospital ECMO team are additional to the standard ECMO team which would not be influenced by the activity. Planning with the theatre schedulers and cardiac surgeons regarding.	2	2	4
Failure to cannulate femoral vessels Expected failure rate of 5-10% of percutaneous cannulation of femoral vessels in cardiac arrest. Failure would negate ability to initiate ECPR.	3	4	12	Experienced consultants, cannulating with the use of ultrasound, Saline fluid infusion to improve vessel size. Augmented reality ultrasound glasses to improve technique. Any failure to cannulate would mean patient would receive standard ongoing care as per LAS resuscitation protocols.	2	4	8
Leg ischaemia – arterial The size of the arterial cannula can impair blood flow to the ipsilateral limb. A distal limb perfusion cannula will be difficult to insert in the pre-hospital environment	3	4	12	Routine insertion of a distal limb perfusing catheter on return to the Barts Health. Use of smaller arterial cannulae (15Fr).	3	2	6

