8.5 Multiple-centre studies

Not applicable

9 Safety analysis

The number of subjects having at least one AE will be presented. The number of subjects with AEs of mild/moderate/severe intensity will be shown as well as the total number of AEs allowing multiple events per patient.

SAEs will be listed along with details including whether the event is unexpected and whether it is thought to be related to the treatment.

10 References

1. Virdi, G., S. Picton, and R. Fothergill *London Ambulance Service NHS Trust Cardiac Arrest Annual Report: 2014/15*. 2015.
2. Fagnoul, D., A. Combes, and D. De Backer, *Extracorporeal cardiopulmonary resuscitation*. Curr Opin Crit Care, 2014. 20(3): p. 259-65.
3. Soar, J., et al., *Adult advanced life support guidelines*. 2015.
4. Keith, R.A., et al., *The functional independence measure: a new tool for rehabilitation*. Adv Clin Rehabil, 1987. 1: p. 6-18.

11 Document history and version control

All versions will be dated and numbered in the format N.x, where N is a numeric value that is increased when a major change is made. The postscript x relates to minor changes typically for typographical errors that do not substantially alter the conduct of the tool.

The full history is outlined in Table 4.

Table 4 Version history

Version	Date	Notes
1.0	10 April 2019	First authorised version of Statistical Analysis Plan

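### Protocol section 16.5 judges expectedness by event type alone and drops Table 9's severity test, so an unusually severe form of a listed SAE can miss expedited reporting

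*Protocol*

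**What the plan says.** Protocol section 16.3 sets the assessment step: "All Serious Adverse Events will be assessed for causality and expectedness, using the definitions in Table 8 and Table 9". The unexpected row of Table 9 has two limbs. The first is anticipation: "Unexpected events are those not anticipated but could relate to the study". The second is severity: "Events that are of a more serious form that would be expected should also be considered as unexpected". The expected row names nine events and adds whatever the product summaries list as undesired effects of the non-investigational medicines. Two of the named entries are "Bleeding at site of cannulation" and "Vascular damage during cannulation in adverse environment"; infection at the cannulation site is another. None of these three carries a grade or an outcome limit.

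Section 16.5 sets the reporting step. An SAE goes to the ethics committee if, in the Chief Investigator's opinion, it is related and also meets this condition: "Unexpected (the type of event is not listed in Table 9"). The same section requires related and unexpected SAEs to reach the sponsor within 24 hours and the ethics committee within 15 days. Separately, it sends every SAE to the trials unit within 24 hours, into the SAE log and into routine reporting to the ethics committee.

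SAP section 9 uses the same classification without defining it: "SAEs will be listed along with details including whether the event is unexpected and whether it is thought to be related to the treatment".

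**The concern.** Expectedness is defined twice, and the definitions differ. Table 9 looks at type and severity. The bracketed definition in 16.5 looks at type only, although it cites Table 9. An assessor who works from 16.5 will treat every occurrence of a listed type as expected, however severe. An assessor who works from 16.3 will not.

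The events affected are the ones where prompt notice is most useful: severe procedural harm from cannulation. Section 4.3 says pre-hospital ECPR has never been performed in the UK, and section 5.2 makes safety of delivery a secondary objective. The label also appears in the SAP's SAE listing, where a reader could not tell which definition had produced it.

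**Working it through.** The plan states no figure on this point, so the check is to apply both rules to the same events. Each event is assumed to be serious and related.

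| Event | Section 16.5 (type only) | Section 16.3 and Table 9 (type and severity) | Same answer? |
|---|---|---|---|
| Site bleed of the kind expected | Listed: not expedited | Expected: not expedited | Yes |
| Unusually severe, non-fatal site bleed | Listed: not expedited | More serious form: expedited | No |
| Unusually severe, non-fatal vessel injury or site infection | Listed: not expedited | More serious form: expedited | No |
| Fatal site bleed | Depends on how the type is named | More serious form: expedited | Unclear |
| Event neither listed nor foreseen | Not listed: expedited | Not anticipated: expedited | Yes |

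**Fatal row.** If the type is bleeding at the site, it is listed, and 16.5 does not expedite it. If the type is death due to bleeding, it is not listed, and 16.5 does expedite it. Table 9 gives some support to the second reading, because it lists hypoxic brain injury and death from hypoxic brain injury as separate entries. The only other death it names is from myocardial failure.

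**Reach of the conflict.** Table 9 names nine expected events, of which two are deaths. That leaves 9 − 2 = 7 named entries, plus the product-summary effects, for which a more serious form could be at issue. Seven is an upper limit, since failure to cannulate is hard to grade.

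**What changes with the rule chosen.**
- Sponsor within 24 hours and ethics committee within 15 days: changes.
- The unexpected label in the SAP section 9 listing: changes.
- Trials unit within 24 hours, SAE log and routine ethics committee reporting: no change.
- Appearance of the SAE in the SAP listing: no change, because all SAEs are listed.
- Complication incidence, which SAP section 3.5 takes from AE and SAE data: no change.

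**Who would catch a difference.** Section 16.5 leaves the decision to the Chief Investigator, who under section 16.8 is also the medical assessor for the sponsor. The trials unit oversees safety reporting and checks that SAEs are identified and reported on time. No separate review of the expectedness call is described.

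**The case against.** The strongest reply is that 16.3 governs. It says which definitions are used to assess expectedness, the severity limb is inside Table 9, and 16.5 itself points to Table 9. The bracket can then be taken as shorthand, and the 24-hour and 15-day sentence acts on SAEs already classified under 16.3. This is a reasonable reading and may be the intended one. It does not remove the problem, because 16.5 states its own test in terms that leave severity out, and nothing says which text prevails.

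The second reply is that little is lost. Every SAE reaches the trials unit within 24 hours, the Chief Investigator reviews all reported events, the monitoring committee can call extra meetings, and urgent safety measures under section 16.6 involve no expectedness test. This stands. It limits the consequence to one reporting route and one label.

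A reader might go further and infer that a fatal cannulation bleed certainly escapes expedited reporting. The documents do not support that: Table 9's separate entries for an event and for death from it allow such a death to count as an unlisted type even under 16.5.

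A reader might also treat the absence of distal leg ischaemia from Table 9 as an error. It is a named complication in section 5.4, and Table 5 gives it its own row, where it is noted that "The size of the arterial cannula can impair blood flow to the ipsilateral limb". Its rating is 3 × 4 = 12 before mitigation and 3 × 2 = 6 after. But foreseeing a risk does not oblige the sponsor to list it as expected, leaving it off errs towards more reporting, and the product summaries that might cover it are not available here.

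**Conclusion.** The point holds as an internal contradiction in current protocol text. For a related SAE that is an unusually severe, non-fatal form of a listed type, section 16.5 read literally and Table 9 give opposite answers on expedited reporting. For a fatal form, the answer under 16.5 is unclear. The result is inconsistent classification, not certain non-reporting.

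The consequence is limited to the sponsor and ethics committee expedited reports and the unexpected column of the SAE listing. No estimate changes, and SAP section 3.7 plans no hypothesis tests. It would be tempting to say that one misclassified death is 17% of the cohort. That is only 1/6, and the documents give no basis for the chance that such a case occurs or is misclassified.

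The conclusion assumes that the 16.5 bracket may be applied as written and that no other trial document settles which definition prevails. The correction is worth making because it concerns severe procedural harm and takes only a few words.

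**What to change.** Replace the bracket in section 16.5 so that it defers to the whole of Table 9, for example: *Unexpected (as defined in Table 9: the event type is not listed, or the event takes a more serious form than expected)*. Have the sponsor state in Table 9 how deaths from causes other than the two listed are classed. Add to SAP section 9 that the unexpected label in the SAE listing uses this same definition.

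The cost is a small wording amendment to each document and possibly a few more expedited reports for severe forms of listed events. Treatment, endpoints and sample size do not change.

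Optionally, and not as a correction, the sponsor may confirm that distal leg ischaemia was left off the expected list on purpose. If it were added, ordinary serious cases would no longer be expedited, while unusually severe ones still would be under the amended definition.
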